1.0 Background

Benign prostatic hypertrophy (BPH) is common with almost 50% of men having pathologic changes in the prostate between 50 and 60 years old¹. There are many options for the treatment of BPH, though a minimally invasive approach has been favorable over the past decade. Enucleation of a prostate with a laser has become a mainstay of BPH treatment and has shown to be safe and effective. Traditionally, a holmium laser is used for this (i.e. Holmium laser enucleation of the prostate or HoLEP), though recent new technologies have been developed to improve laser surgery. One example is the Moses laser fiber produced by Lumenis (Yokneam, Israel), which alters laser pulse wave characteristics to improve the efficiency of energy delivery to a target. The technology is hypothesized to lead to better improvements in operative time and hemostasis ^{2,3,4}. Though the technology has been proven to be safe in human use, it has not been formally evaluated for prostatic enucleation. We seek to compare HoLEP to Moses laser enucleation of the prostate (i.e. MoLEP) for the treatment of BPH.

1. Berry SJ, Coffey DS, Walsh PC, Ewing LL. The development of human benign prostatic hyperplasia with age. *J urol* 1084; 132(3):474-479.
3. Mark Cynk, Holmium Laser Enucleation of the Prostate is More Efficient with More Laser Power, abstract #MP7- 01, Moderated Poster Session 7: BPH/LUTS, WCE 2016

2.0 Rationale and Specific Aims

The aims of this study are to:

1. Evaluate Moses laser technology for prostatic enucleation compared to traditional holmium laser enucleation.
2. Determine changes in blood loss, operative times, and quality of life improvements between the two technologies.

3.0 Animal Studies and Previous Human Studies

There are no previously published articles examining animal studies related to Moses fiber enucleation of the prostate. Currently, laser enucleation of the prostate with standard holmium or thulium lasers is routinely performed for BPH. Though Moses technology operates similar to other lasers on the market and has been shown to be safe in humans, it has not been evaluated for surgical outcomes.

4.0 Inclusion/Exclusion Criteria

- Exclusion criteria
 - 1. Pediatric patients (<18 years old)
 - 2. Abnormal anatomy precluding enucleation
- Inclusion
 - 1. Patients with planned prostatic enucleation for BPH.

5.0 Enrollment/Randomization

We will identify patients scheduled to undergo laser enucleation of the prostate for BPH through our urology clinic. Power analysis to detect a 50% change in blood loss (i.e. a change in hemoglobin level) will lead to approximately 20 patients in each group. A random number generator will be used at the beginning of each case after the induction of anesthesia to randomize patients to MoLEP or HoLEP.

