6.0 Study Procedures

Patients will be consented in our clinic after being scheduled for surgery. All patients will fill out voiding symptom scores (i.e. International Prostate Symptom Scores(IPSS)), erectile dysfunction symptom scores (i.e. Sexual Health Inventory for Men(SHIM)) and have a preoperative urine flow, postvoid volume and a prostate specific antigen (PSA) recorded. Intraoperatively, total surgery time, as well as enucleation and morcellation times, will be recorded. Furthermore, intraoperative blood loss and surgical complications will be evaluated. Postoperatively, all patients will be observed overnight in the hospital with a urethral catheter. Routine labs will be sent including a complete blood count and metabolic panel. Postoperative day one, all patients will undergo a voiding trial for catheter removal. Patients will be monitored for routine complications after HoLEP such as urinary retention, urosepsis, urinary leakage. Other variables to be recorded will be age, sex, size of prostate, BMI, anticoagulation status, and other comorbidities. Patients will follow up at 4 weeks for a postoperative check and evaluation of symptoms (i.e. IPSS, SHIM, flow rate, postvoid residual volume and PSA).

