Vanderbilt University Medical Center
Department of Urologic Surgery
[REDACTED]
[REDACTED]

Statistical Analysis Plan
Date: 12/21/2021

NCT04263987

**Evaluation of the Moses Laser for Prostate
Enucleation**

[name]

Clinical Instructor of Urologic Surgery
Vanderbilt University Medical Center
Department of Urologic Surgery

Power and Statistical Analysis

Power analysis was performed for sample size estimation based on prior reports from the literature, which previously estimated a 20% improvement in operative time when performing M-HoLEP. A sample size of 60 subjects had greater than 80% power to detect this change with $\alpha=0.05$. Continuous and categorical variables were compared using the Student T-test (2-tailed) and Fisher exact test, respectively. Multiple linear regression was performed to evaluate for the effect of the MOSES technique on operative time controlling for age, Charlson comorbidity index, change in hematocrit, and the amount of prostatic tissue enucleated. All testing was performed with $p < 0.05$ as significant. All analyses were conducted in Stata 14.2 (StataCorp, College Station, Texas).

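### With allocation by a per-case draw in 40 to 60 patients, the treatment comparisons should adjust for preoperative prostate size, which no planned analysis uses

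*Protocol*

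**What the plan says.** **Allocation.** Protocol 5.0 states: "A random number generator will be used at the beginning of each case after the induction of anesthesia", to assign MoLEP or HoLEP. Neither document gives an allocation ratio, blocks or strata.

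**Size.** The same section plans "approximately 20 patients in each group", based on a 50% change in blood loss, taken as hemoglobin change. The SAP instead powers on a 20% gain in operative time: "A sample size of 60 subjects had greater than 80% power to detect this change". It does not state group sizes.

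**Prostate size.** The only exclusions in Protocol 4.0 are age under 18 and anatomy that rules out enucleation. Protocol 6.0 does collect size: "Other variables to be recorded will be age, sex, size of prostate, BMI, anticoagulation status". Neither document uses it as a stratum or a covariate.

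**Analysis.** The SAP states: "Continuous and categorical variables were compared using the Student T-test (2-tailed". It adds one multiple regression, for operative time, with age, the Charlson index, hematocrit change and the amount of tissue removed as covariates. It describes no adjusted analysis for blood loss or hemoglobin.

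**The concern.** Larger glands can be expected to take longer to enucleate. A per-case draw with no restriction leaves the balance of gland size to chance, and a trial this small cannot be relied on to even it out. If one arm happens to get the larger glands, the unadjusted comparison mixes the laser effect with that difference, and readers will discount the result in either direction.

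The usual remedy is to adjust for the baseline variable. The SAP regression comes close but uses the wrong measurements. Tissue removed and hematocrit change are both observed after allocation, and the laser may affect both. Protocol 2.0 lists blood loss among the outcomes to be compared. Conditioning on such variables can remove or distort part of the effect being estimated. Preoperative size cannot be affected by the laser, so it is the safe covariate.

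**Working it through.** **1. The plan's own figures.** Neither sample size can be reproduced, because no SD is given. I back-solved with a noncentral t, two-sided 5% and 80% power (80% is assumed for the protocol).
- 20 per arm detects 0.909 SD. A 50% change then implies a coefficient of variation of 0.50/0.909 = 0.55.
- 30 per arm (equal split of the SAP's 60 assumed) detects 0.736 SD. A 20% change then implies 0.20/0.736 = 0.27.

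**2. Group sizes.** Under an unrestricted 1:1 draw (assumed), the size of one arm is Binomial(N, 0.5).

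| | N = 40 | N = 60 |
|---|---|---|
| Chance of an exactly equal split | 12.5% | 10.3% |
| Chance of an uneven split | 15/25 or worse: 15.4% | 24/36 or worse: 15.5% |
| Power at that split (80% if equal) | 77.4% | 78.4% |
| Power averaged over all splits | 79.0% | 79.3% |

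**3. Chance imbalance in prostate size.** With n per arm, the standardised difference D has SE = sqrt(2/n), and P(|D| > c) = 2[1 − Φ(c/SE)].
- n = 20: SE = 0.316. For c = 0.25, c/SE = 0.79, giving 43%. For c = 0.5, c/SE = 1.58, giving 11%.
- n = 30: SE = 0.258. For c = 0.25, c/SE = 0.97, giving 33%. For c = 0.5, c/SE = 1.94, giving 5%.

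**4. Effect on the unadjusted difference.** Given D, the shift is r × D outcome SDs, where r is the correlation between size and outcome. The documents give no r, so I take 0.3 to 0.7. For D = 0.25:

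| r | Shift (SD) | Share of 0.736 SD (n = 30) | Share of 0.909 SD (n = 20) |
|---|---|---|---|
| 0.3 | 0.075 | 10% | 8% |
| 0.5 | 0.125 | 17% | 14% |
| 0.7 | 0.175 | 24% | 19% |

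**5. Validity of the t-test.** Over all randomizations, simulated type I error is 4.9% to 5.1% at r = 0.5 and 0.7. Given D, the difference has mean rD and SD sqrt(1 − r²) × SE, but it is judged against 1.96 × SE. For n = 30, r = 0.5 and D = 0.5, the mean is 0.25, the SD is 0.866 × 0.258 = 0.224 and the cutoff is 1.96 × 0.258 = 0.506. Then (0.506 − 0.25)/0.224 = 1.14, a conditional error of about 13%. It is 8% at r = 0.3 and 20% at r = 0.7. At D = 0.2 the same formula gives 4.6%, 3.8% and 2.4% for r = 0.3, 0.5 and 0.7. The excess at large imbalances is offset by a deficit at small ones.

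**6. What adjustment recovers.** A baseline covariate multiplies the residual SD by sqrt(1 − r²). By the normal approximation, power becomes Φ[(1.96 + 0.84)/sqrt(1 − r²) − 1.96].
- r = 0.3: 2.80/0.954 − 1.96 = 0.98, giving 84%.
- r = 0.5: 2.80/0.866 − 1.96 = 1.27, giving 90%.
- r = 0.7: 2.80/0.714 − 1.96 = 1.96, giving 98%.

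Putting the t-based 0.909 SD into the normal formula gives 91% at r = 0.5. That is slightly generous, since the same mixture gives 82% without the covariate. The degree of freedom spent on the covariate takes a little off all three figures.

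**The case against.** Several stronger readings are tempting, and the documents do not support them.

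- **The t-test is biased or invalid.** It is not. Its standard error already includes variation due to prostate size, and its overall level holds (step 5). The shift in step 4 is sampling error conditional on a particular imbalance.
- **The plan fails to secure 20 per group.** Protocol 5.0 says only approximately 20, and uneven splits cost about 1 power point on average. With 60 patients, both arms reach 20 with probability 99.4%.
- **Allocation is not concealed.** Consent is taken in clinic and the draw follows induction, so there is no upcoming assignment to foresee at enrollment. No log, or person responsible for the draw, is described, but an undetected redraw is an inference from silence in a very short protocol.
- **Stratified blocks are needed.** Simple randomization is valid. Blocks add some predictability where operators know past assignments.
- **The t-test is the main analysis.** The SAP names no primary analysis. The regression is the only analysis tied specifically to the laser effect on operative time, and tissue removed is related to gland size, so it gives partial protection.

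That last point reduces the exposure for operative time but does not remove it, because the covariate is measured after allocation. It offers nothing for hemoglobin. It is also fair that the size of the problem rests on an assumed correlation, and that the SAP claims more than 80% power. The planned effect may therefore exceed 0.736 SD, and the n = 30 percentages in step 4 are then upper bounds for each correlation.

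**Conclusion.** The concern holds as one of precision and interpretation. A noticeable imbalance in prostate size is likely (more than 0.25 SD in 33% to 43% of trials), a large one is possible (more than 0.5 SD in 5% to 11%), and no planned analysis adjusts for size as it stood before allocation. Given a 0.25 SD imbalance with 60 patients, the shift in the operative-time difference is about 10% to 24% of the detectable effect.

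This rests on an unrestricted 1:1 draw, which is the natural reading of Protocol 5.0 but is not stated, and on a correlation of 0.3 to 0.7. It also reads the recorded prostate size as a preoperative measurement, which Protocol 6.0 implies by listing it with age and BMI but does not say outright. It does not support a claim that the randomization is invalid or that the false-positive rate is inflated overall.

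**What to change.** In the SAP, make the main treatment comparison for operative time, and separately for hemoglobin change, a linear model with arm and preoperative prostate size. Age and the Charlson index can be kept if wanted. Move the models containing tissue removed and hematocrit change to sensitivity analyses. State in Protocol 6.0 that size is measured before surgery, and how. The SAP is written in the past tense; if the data have already been analysed, report the new model as an added analysis and label it so.

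The cost is a few sentences and one degree of freedom, with no extra patients. No extra data are needed if size is already measured preoperatively.

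Optional: state the 1:1 ratio and log each draw, keeping the reveal after induction. Stratified permuted blocks are a design preference. If they are used, the model must include prostate size: at 60 patients, stratification followed by an unadjusted t-test makes the test conservative, with simulated type I error of about 4.4% at a correlation of 0.3, 3.6% at 0.5 and 2% at 0.7.

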6.0 Study Procedures

Patients will be consented in our clinic after being scheduled for surgery. All patients will fill out voiding symptom scores (i.e. International Prostate Symptom Scores(IPSS)), erectile dysfunction symptom scores (i.e. Sexual Health Inventory for Men(SHIM)) and have a preoperative urine flow, postvoid volume and a prostate specific antigen (PSA) recorded. Intraoperatively, total surgery time, as well as enucleation and morcellation times, will be recorded. Furthermore, intraoperative blood loss and surgical complications will be evaluated. Postoperatively, all patients will be observed overnight in the hospital with a urethral catheter. Routine labs will be sent including a complete blood count and metabolic panel. Postoperative day one, all patients will undergo a voiding trial for catheter removal. Patients will be monitored for routine complications after HoLEP such as urinary retention, urosepsis, urinary leakage. Other variables to be recorded will be age, sex, size of prostate, BMI, anticoagulation status, and other comorbidities. Patients will follow up at 4 weeks for a postoperative check and evaluation of symptoms (i.e. IPSS, SHIM, flow rate, postvoid residual volume and PSA).

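### The protocol's power statement and the SAP's regression covariate both need a preoperative blood count, but Section 6.0 schedules a count only after surgery

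*Protocol*

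**What the plan says.** **Sizing.** Protocol Section 5.0 reads "Power analysis to detect a 50% change in blood loss (i.e. a change in hemoglobin level") and states that this "will lead to approximately 20 patients in each group". It gives no mean change, SD, alpha or power.

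**Before surgery.** Protocol Section 6.0 lists IPSS, SHIM, and patients who "have a preoperative urine flow, postvoid volume and a prostate specific antigen (PSA) recorded". A blood test is on that list (PSA), but no hemoglobin, hematocrit or blood count.

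**After surgery.** The same section continues: "Postoperatively, all patients will be observed overnight in the hospital with a urethral catheter". The next sentence is "Routine labs will be sent including a complete blood count and metabolic panel". This is the only blood count in the protocol. The background variables ("Other variables to be recorded will be age, sex, size of prostate, BMI, anticoagulation status, and other comorbidities") do not include one, nor does the 4-week visit.

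**During surgery.** Section 6.0 also says that "intraoperative blood loss and surgical complications will be evaluated", without giving a method, and it records total, enucleation and morcellation times.

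**SAP.** The power statement is for a 20% improvement in operative time with 60 subjects. Continuous variables are compared by a two-tailed t-test. The multiple regression of operative time includes "change in hematocrit" as a covariate.

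**The concern.** A change score needs a value before and a value after. The protocol uses such a change to justify its sample size, and the SAP uses one as a covariate, yet the written schedule supplies only the second value. A site following Section 6.0 to the letter would have no study baseline. A site filling the gap from the chart would use values of differing age, with no rule on which value counts or how old it may be.

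Two things are at stake. First, for the hemoglobin comparison, a missing baseline leaves only the postoperative value, which carries all the between-patient variation. Chart values from mixed dates add noise and missing data. Second, the SAP does not say how missing covariates are handled, so a patient without a baseline would drop out of a complete-case operative-time regression.

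**Working it through.** **1. What each quantity needs and what is scheduled**

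| Quantity | Where used | Preoperative value scheduled? | Postoperative value scheduled? |
|---|---|---|---|
| Change in hemoglobin | Protocol 5.0, sample size | No | Yes, in the blood count |
| Change in hematocrit | SAP, regression covariate | No | Yes, in the blood count |
| Operative time | SAP, power and regression outcome | Not needed | Recorded during surgery |
| Intraoperative blood loss | Protocol 6.0 | Not needed | Evaluated during surgery, method not stated |

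The first two rows lack an input. The last two do not.

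**2. The plan's own figure.** The 20 per group cannot be reproduced, because Section 5.0 gives no SD, alpha or power. It can be solved backwards. At two-sided 0.05 and 80% power (both assumed for the protocol), 20 per group detects a standardised difference of d = √(2/20) × (1.960 + 0.842) = 0.886 by the normal approximation, or 0.909 by the t distribution. A 50% difference then implies SD/mean = 0.5/0.909 = 0.55. The stated figure is attainable but cannot be verified.

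**3. What a missing baseline could cost.** Assumptions, none of them in the documents: exactly 80% power on the change score at 20 per arm (d = 0.909), equal pre and post SDs σ, and a pre/post correlation r.

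- SD of the change: σ√(2(1−r))
- SD of the postoperative value alone: σ
- Residual SD with baseline as covariate: σ√(1−r²)

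Randomisation makes the expected arm difference the same in all three analyses, so only the SD changes:

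- postoperative value alone: d_post = 0.909 × √(2(1−r))
- baseline-adjusted: d_adj = 0.909 × √(2(1−r))/√(1−r²) = 0.909 × √(2/(1+r))

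Worked case, r = 0.8: d_post = 0.909 × 0.632 = 0.575, and d_adj = 0.909 × 1.054 = 0.958. Power comes from the noncentral t distribution, 20 per arm, two-sided 0.05. The one degree of freedom used by the covariate is ignored.

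| r | d_post | Power, post only | d_adj | Power, adjusted |
|---|---|---|---|---|
| 0.5 | 0.909 | 80% | 1.050 | 90% |
| 0.6 | 0.813 | 71% | 1.016 | 88% |
| 0.7 | 0.704 | 58% | 0.986 | 86% |
| 0.8 | 0.575 | 43% | 0.958 | 84% |
| 0.9 | 0.407 | 24% | 0.933 | 82% |

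At r = 0.5 the postoperative value alone matches the change score. Below 0.5 it does better: about 91% at r = 0.3.

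**4. At the SAP's total of 60.** With an equal split assumed (30 per arm) and the same d, post-only power is about 87%, 76%, 59% and 34% at r = 0.6, 0.7, 0.8 and 0.9.

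**The case against.** **A reader might infer that the hemoglobin change cannot be computed at all.** The documents do not support that. The count is described as a routine lab, and the SAP says in the past tense that a regression using change in hematocrit was performed, which suggests that chart baselines existed. Section 6.0 is also a short narrative, not a full data form: the SAP uses the quantity of tissue removed, which Section 6.0 does not list either. So silence there is weak evidence that a value was never obtained. What stands is narrower. No passage says where the baseline comes from, which value counts, or how old it may be.

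**A reader might infer that blood loss then rests on postoperative hemoglobin alone.** It does not. Aim 2 in Section 2.0 names blood loss, not hemoglobin, and intraoperative loss is evaluated. That measure does not close the gap in Section 5.0, which defines its outcome as a hemoglobin change.

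**A reader might infer that the SAP's powered outcome is missing.** It is operative time, and Section 6.0 records it. Hematocrit enters the SAP by name only as a covariate.

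**The power loss is a worst case.** This stands. The table assumes that nobody has a baseline, and r is assumed. The likelier case, chart values at mixed dates, cannot be priced from the documents.

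**The postoperative draw is roughly bracketed.** This also stands. The labs sentence falls between the overnight stay and the day-one voiding trial. But no single time is set for both arms.

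**Conclusion.** The concern holds as a gap in specification. The preoperative count needed by the protocol's power statement and by the SAP's covariate is not in the written schedule, so it is absent or comes from the chart at an unstated date. The documents cannot show which.

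If no baseline existed, power on the hemoglobin comparison would fall from the assumed 80% to between 71% and 24% for r between 0.6 and 0.9, with no loss at 0.5 and a gain over the change score below that. Baseline adjustment gives 88% to 82% over the same range, and exceeds the postoperative value alone at every r from 0.3 to 0.9 that was computed. The recommendation therefore does not depend on the assumed r, although the size of the benefit does. The SAP's operative-time outcome and its unadjusted comparison are unaffected; the adjusted regression is affected only through its covariate. The point should be addressed, and it is cheap to address.

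**What to change.** - Add hemoglobin or hematocrit to the preoperative list in Section 6.0, with one collection window for all patients. Use the same analyte in the protocol and the SAP.
- State one collection time for the postoperative count, the same in both arms.
- In the SAP, compare arms on the postoperative value by linear regression with the preoperative value as covariate, in place of the unadjusted t-test for this outcome.
- If data collection is finished, use the chart baseline, state its date window, report by arm how many patients lack it, and apply the same regression.

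Cost: one line in the procedures and on the data form, and at most one routine blood count per patient, which can be drawn with the other preoperative bloods. No extra patients are needed. If collection is over, the cost is a chart review of dates and values.

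### Anticoagulation status is recorded, but no blood-loss analysis adjusts for it: a modest, assumption-dependent loss of precision and no protection against chance imbalance

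*Protocol*

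**What the plan says.** **Eligibility.** Protocol section 4.0 admits "Patients with planned prostatic enucleation for BPH". Its two exclusions are age under 18 and "Abnormal anatomy precluding enucleation". Neither concerns anticoagulation, so anticoagulated men can enter.

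**Data collected.** Section 6.0: "Other variables to be recorded will be age, sex, size of prostate, BMI, anticoagulation status, and other comorbidities". Anticoagulation status will therefore be available for analysis, although its definition and coding are not given.

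**Allocation.** Section 5.0: "A random number generator will be used at the beginning of each case after the induction of anesthesia to randomize patients to MoLEP or HoLEP". No stratification or blocking is stated.

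**Role of blood loss.** The second aim in section 2.0 is: "Determine changes in blood loss, operative times, and quality of life improvements between the two technologies". Section 5.0 sizes the trial on it: "Power analysis to detect a 50% change in blood loss (i.e. a change in hemoglobin level) will lead to approximately 20 patients in each group". The SAP instead bases its 60 subjects on operative time, citing literature "which previously estimated a 20% improvement in operative time when performing M-HoLEP".

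**Analysis.** The SAP says: "Continuous and categorical variables were compared using the Student T-test (2-tailed) and Fisher exact test, respectively". Blood loss is not named in that sentence, but no other method in the SAP covers it as an outcome. The only regression has operative time as its outcome. Its covariates are age, Charlson index, hematocrit change and amount of tissue removed; anticoagulation is not among them.

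**The concern.** The trial collects a preoperative characteristic with an obvious link to bleeding and then does not use it where it matters most. The plan adjusts operative time for four variables but compares blood loss with no adjustment at all.

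Two things are at stake. First, variation in blood loss that anticoagulation could explain stays in the error term, so the interval for the arm difference is wider than it need be. Second, with 20 to 30 patients per arm and no stated stratification, one arm may by chance hold noticeably more anticoagulated men. The t-test cannot take account of a visible imbalance of that kind, and readers of the one trial that is run would have to judge its influence by eye.

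**Working it through.** **1. The plan's own figures.** Neither sample size can be reproduced. No mean, SD or coefficient of variation (CV) is given for either outcome, and the protocol states no power. Solving backwards at 80% power and two-sided 5%:

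- At 20 per group the detectable standardised difference is (1.960 + 0.842) × √(2/20) = 0.886, or 0.909 with the t distribution. A 50% change then implies a blood-loss CV of 0.5/0.886 = 0.56, or 0.5/0.909 = 0.55.
- At 30 per group (60 subjects, equal arms assumed) the detectable difference is 0.723, or 0.736 with the t distribution. A 20% change then needs an operative-time CV of at most 0.2/0.723 = 0.28, or 0.2/0.736 = 0.27.

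These set the scale, but they say nothing about anticoagulation.

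**2. Assumed inputs (not in the documents).** Prevalence p from 10% to 35%. Extra blood loss in anticoagulated men d from 0.5 to 1.0 within-group SD. Total N of 40 or 60.

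**3. Chance of imbalance.** Probability that the arms differ by 20 points or more:

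- Exact binomial, fixed equal arms, p = 15% to 35%: 12% to 25% at 20 per arm, 5% to 14% at 30 per arm.
- Simulation, each patient randomised independently, p = 10% to 30%: 4% to 18% at N = 40, 1% to 10% at N = 60.

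**4. Size of the shift.** A 20-point imbalance moves the arm difference by 0.20 × d, that is 0.1 to 0.2 SD. The standard error of the difference is √(2/20) = 0.32 SD or √(2/30) = 0.26 SD. The shift is thus between 0.1/0.32 = 0.3 and 0.2/0.26 = 0.8 of one standard error.

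**5. Standard error saved by adjustment.** Saving = 1 − 1/√(1 + p(1 − p)d²), before the degree of freedom is paid for:

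| p | d | p(1 − p)d² | Saving |
|---|---|---|---|
| 0.10 | 0.5 | 0.0225 | 1.1% |
| 0.15 | 0.5 | 0.0319 | 1.6% |
| 0.10 | 1.0 | 0.0900 | 4.2% |
| 0.35 | 1.0 | 0.2275 | 9.7% |

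**6. Error rates and power.** These come from 40,000 simulated trials per scenario, with p = 10%, 20% and 30% and simple randomisation. They compare the two-sided t-test with a linear model that adds a yes/no anticoagulation term.

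| Quantity | t-test | Adjusted |
|---|---|---|
| Overall type I error | 4.8% to 5.2% | 4.8% to 5.1% |
| Type I error given imbalance ≥ 20 points, d = 0.5 | 5.8% to 7.3% | 4.3% to 5.8% |
| Type I error given imbalance ≥ 20 points, d = 1.0 | 9.5% to 13.3% | 4.7% to 5.8% |
| Power, N = 40 | about 77% | 77% to 83% |
| Power, N = 60 | about 78% | 78% to 85% |

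The mean error of the unadjusted difference was about zero in every scenario. The power gain is about 0 to 2 points at d = 0.5 and 2 to 7 points at d = 1.0. At N = 40, p = 10% and d = 0.5 there is no gain (76.9% against 76.5%).

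**The case against.** A reader might infer that the blood-loss comparison is biased or its error rate inflated. The documents do not support that. Allocation is random, so chance imbalance is part of the sampling variation that the t-test's standard error already covers; overall type I error stays near 5% and the mean bias is about zero.

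A reader might also blame open eligibility. It applies equally to both arms and reflects the men who are treated, so it is not a flaw. Nor does adjustment avoid an imbalance, which only restricted allocation could do; it corrects the estimate for the imbalance that occurs.

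Three further objections carry weight:

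- **The size rests on assumptions.** The documents give no prevalence, no effect on hemoglobin and no definition of anticoagulation status. It could mean history of use, current use or use at surgery. If the effect is below 0.5 SD, the gain is smaller than shown.
- **Other covariates have a claim.** Age and prostate size may also predict blood loss, and a sensitivity analysis would answer much of the point. Anticoagulation has the plainest link to bleeding among the variables listed, but that is a judgement.
- **The status of blood loss is unsettled.** The protocol sizes the trial on it, while the SAP powers on operative time. The documents should be reconciled on which outcome is primary.

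None of this removes the case for using a baseline variable that the trial already collects. It limits how much should be claimed.

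**Conclusion.** The point holds as a cheap improvement and not as a validity failure. Anticoagulation status is recorded, is not a stated stratification factor, and appears in no SAP analysis of blood loss. The planned t-test is valid on average. What is lost is about 1% to 10% in standard error and 0 to 7 points of power. There is also no protection in the minority of trials imbalanced by 20 points or more, where the conditional false-positive rate is about 6% to 13% against 4% to 6% with adjustment. The upper ends require a 1.0 SD effect; at 0.5 SD the benefit is slight and may be nil at low prevalence. All these figures depend on an assumed prevalence and effect, so they show a plausible range and do not estimate what will happen in this trial.

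**What to change.** Leave the eligibility criteria as they are. In the SAP:

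- Name hemoglobin or hematocrit change and recorded blood loss as outcomes.
- Analyse each by linear regression on treatment arm and preoperative anticoagulation status, and define how that status is coded.
- Report the adjusted arm difference with its 95% CI beside the t-test result.

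The SAP is written in the past tense. If outcome data had already been seen when this analysis is added, label the adjusted result as not prespecified.

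The cost is a short addition to the SAP and one degree of freedom per model. No extra patients, procedures or data items are needed. The downside is that the gain may turn out to be small.
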